## **Study description**

### **Brief Summary**

Crohn’s disease (CD) related strictures can be treated endoscopically by endoscopic balloon dilation (EBD) or endoscopic stricturotomy (EST). EBD is the established endoscopic treatment for short strictures in Crohn's disease. However, roughly half had recurrent symptoms and two third require surgery after EBD. ES have been used initially for endoscopic treatment of patients for whom EBD was unsuccessful. Subsequently it was shown that ES is a better modality for treating CD related strictures (specially short and anastomotic strictures) than EBD lowering the risk of future surgery and procedure related perforation albeit with an increased risk of bleeding. ES was shown to be non-inferior to re-do surgery in chronic pouch anastomotic sinus in ulcerative colitis (UC) and ileocolic anastomotic strictures in CD thus reducing surgical morbidity. However, these two modalities have not been compared in a randomized controlled manner. We aimed to compare the two endoscopic treatments with regard to clinical success, need for surgery or additional endoscopic procedure and safe-

ty in patients with CD who have short (<3 cm), predominantly fibrotic stenosis excluding those in the small bowel not accessible by endoscope/colonoscopy.

Condition or disease	Intervention or treatment
Crohn's disease	Intervention: Endoscopic balloon dilation
	Intervention: Endoscopic stricturotomy

#### **Detailed description**

**Study design:** Single centre, open-label, randomized trial to be done in Asian Institute of Gastroenterology, India

**Study population:** All eligible consecutive patients with CD who developed DE-nova or anastomotic strictures will be included.

#### **Study settings:**

The proposed study would be conducted in a high volume tertiary GI centre (Asian Institute of Gastroenterology) performing nearly more than 200 EBD/ES procedures per year with an well established inflammatory bowel disease (IBD) registry with more than 7000 IBD patients under follow up.

The study will be conducted after approval by the institutional ethics committee. Written informed consent would be taken from each participants and the study would conform to the 1975 Declaration of Helsinki ethical guidelines.

**Data collection:** A survey administration software (google forms) would be used to collect the participant data (age, sex, ethnicity, clinical features, smoking status, details of CD diagnosis, disease phenotype, extra intestinal manifestations, family history, history of intestinal resection, details of stricture diagnosis, details of stricture: degree, number, location, radiological finding: concurrent abscess, fistula, enhancement;

drug history for CD, procedural details: technical success, symptomatic improvement, endoscopic improvement, stricture related emergency visit or hospitalization, complications, subsequent need for additional endoscopic procedures or surgery upto a follow up of 1 year). Follow-up details would be collected via physical visit or telephonic communication.

**Technique and instruments:** EBD procedures will be performed with wire guided CRE pneumatic balloon (controlled radial expansion balloon, Boston scientific, Marlborough, MA, USA) of various sizes based on tightness of the stricture (10-12 mm, 12-15 mm, 15-18 mm, 18-20 mm) with graded dilation with inflation pressures varying from 3-8 ATM pressure. Balloon was inflated for at least 2 minutes and slowly deflated. For mild ooze post EBD, balloon tamponade will also be done with the same balloon. A maximum of two sessions of dilation will be allowed with a minimum interval of 15-30 days between them. Additional EBD sessions would be considered as additional endoscopic procedure for the purpose of the study.

Endoscopic stricturotomy would be done using a needle knife/insulted tip (IT) knife with the following electrocautery settings : Endocut Q (effect 3, cut duration 1, cut interval 3) as per by global IIBD group consensus.

**Definitions:** Technical success for EBD was defined as ability to perform the EBD procedure. Scope passage after EBD/stricturotomy was assessed as a separate outcome which was defined as passage of endoscope through the area where EBD/ES was performed. This included colonoscopy for colonic/pouch strictures, endoscope for upper GI and duodenal strictures and an endoscope: motorized spiral or single balloon enteroscopy for small bowel strictures except those in terminal ileum. Clinical

success in EBD/ES was defined as clinical improvement in symptoms (pain/ intestinal, gastric outlet or colonic obstruction symptoms) after the procedure. Sustained clinical success was defined as absence of obstructive symptoms at 1 year follow up. Major adverse events were defined as perforation, bleeding requiring transfusion or any procedure related prolongation of hospitalization period or an endoscopic, radiologic or surgical intervention. Minor adverse events were bleeding not requiring blood transfusion, post procedural pain and any other self limiting complication (e.g., sore throat after spiral enteroscopy) which does not warrant prolongation of hospital stay. Adverse events will be recorded for all the patients; events were considered associated to be with the procedure when a causal association was possible, probable, or definite. Recurrence of symptoms would be defined as re-emergence of symptoms for which the procedure was initially performed.

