**Arms and interventions:**

Arm	Intervention/treatment
Active comparator:  Confirmed Crohn's disease with gastro-duodenal or ileo-colonic short (<3 cm) strictures (both de novo and anastomotic) without prior history of endoscopic stricture therapy	Intervention: Endoscopic balloon dilation  EBD procedures will be performed with wire guided CRE pneumatic balloon (controlled radial expansion balloon, Boston scientific, Marlborough, MA, USA) of various sizes based on tightness of the stricture (10-12 mm, 12-15 mm, 15-18 mm, 18-20 mm) with graded dilations with inflation pressures varying from 3-8 ATM pressure. Balloon was inflated for at least 2 minutes and slowly deflated. A maximum of two sessions of dilation will be allowed with a minimum interval of 15-30 days between them.

Active comparator	Intervention: Endoscopic stricturotomy with or without stricturoplasty
Confirmed Crohn's disease with gastro-duodenal or ileo-colonic short (<3 cm) strictures (both de novo and anastomotic) without prior history of endoscopic stricture therapy	Endoscopic stricturotomy would be done using either a tri- ple-lumen needle-knife (Boston Scientific, Marlborough, MA) or with a electrosurgical IT knife2 (Olympus Medical Systems, Tokyo, Japan) in the setting of ERCP Endocut on ERBE (USA Incorporated Surgical Systems, Marietta, GA) with the following electrocautery settings: Endocut Q (effect 3, cut duration 1, cut interval 3). Strictures will be incised in a circumferential or radial fashion until an adequate passage of the scope. Endoclips may be applied post stricturotomy to act as keep treated stricture open and to prevent delayed bleeding (referred as stricturoplasty). Choice of endoclips and decision to perform stricturoplasty would be at the discretion of endoscopist.

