### **Secondary outcome measures**

1. To compare need for additional intervention (EBD/EST/Surgery) between EST and EBD arm (%) : the percentage of patients who require additional interventions for CD related stenosis over period of 1 year
2. To compare technical success between EBD and ES (%): Percentage of patients in whom endoscope is passable after EBD/ES
2. To compare stricture related visit to the emergency department after EST versus EBD: percentage of patients visiting the emergency department for CD stenosis related symptoms post EBD/ES over period of 1 year
3. To compare structure related hospitalization with EST versus EBD: percentage of patients visiting undergoing hospitalization for CD stenosis related symptoms post EBD/ES over period of 1 year
4. To compare complications related to EST versus EBD: Major adverse events will be defined as perforation, bleeding requiring transfusion or any procedure related prolongation of hospitalization period or an endoscopic, radio logic or surgical intervention. Minor adverse events were bleeding not requiring blood transfusion, post procedural pain and any other self limiting complication which does not warrant prolongation of hospital stay. Adverse events were considered associated to be with the procedure when a causal association was possible, probable, or definite.

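### The major/minor adverse event definitions do not count a procedure-related readmission, so a delayed bleed managed conservatively after discharge may be graded minor

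*Protocol*

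**What the plan says.** The Definitions paragraph (Protocol, Study settings) and item 4 of Secondary outcome measures give the same grading rule.

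- **Major:** perforation, bleeding that needs transfusion, or "any procedure related prolongation of hospitalization period or an endoscopic, radiologic or surgical intervention".
- **Minor:** "Minor adverse events were bleeding not requiring blood transfusion, post procedural pain and any other self limiting complication", with an example in the Definitions paragraph and then the closing qualifier "which does not warrant prolongation of hospital stay".

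Neither place mentions a readmission or a new admission after discharge.

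Two other secondary outcomes concern hospital contact. The emergency outcome is the "percentage of patients visiting the emergency department for CD stenosis related symptoms post EBD/ES over period of 1 year". The hospitalisation outcome (item 3) is the "percentage of patients visiting undergoing hospitalization for CD stenosis related symptoms post EBD/ES over period of 1 year". Both are limited to stenosis symptoms. The Data collection paragraph has the same limit: the emergency visits and hospital admissions it lists are the stricture-related ones. Complications are listed as a separate field, and "Adverse events will be recorded for all the patients".

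**The concern.** Prolonging a stay means extending one that has not ended. A patient discharged after the procedure and admitted again some days later has a new stay. On the plain reading, similar harm is therefore graded by when it appears: major if it delays the first discharge, minor if it brings the patient back, provided it is managed without transfusion or intervention.

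The comparison of complications is a declared secondary outcome, and the gap is unlikely to fall equally on the two arms. The Brief Summary expects more bleeding with stricturotomy, and the EST arm description allows clips partly to guard against delayed bleeding. Under-graded events would then tend to sit in the EST arm and make its major-event rate look better than the patients' course warrants.

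The trial is open label (Study design, Masking). If the wording leaves room for judgement, staff who know the allocation will exercise it.

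**Working it through.** **Step 1: the definitions applied to concrete courses.** No figure in the plan depends on this rule, so the main check is to read the definitions against each other.

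| Course | Literal grade | Counted as an emergency visit or hospitalisation outcome? |
|---|---|---|
| Non-transfused bleed, one extra night before first discharge | Major (prolongation) | No |
| Non-transfused bleed or pain after discharge, readmitted for observation only | Minor (named in the minor list; no major criterion met) | No (not a stenosis symptom) |
| Bleed after discharge, readmitted and transfused | Major (transfusion) | No |
| Bleed after discharge, readmitted with endoscopic, radiologic or surgical treatment | Major (intervention) | No |
| Obstructive symptoms after discharge, readmitted | Outside this point | Yes |

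Only the second row is a problem. Its admission lowers no grade, raises no grade and enters no outcome.

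**Step 2: the qualifier.** The closing clause on prolonged stay can attach to the last item only (other self-limiting complications) or to all three items, bleeding and pain included. On the first reading, row 2 is minor. On the second, it is minor if a readmission is not a prolongation, and unclassified or major if an assessor treats it as one. The text does not settle which reading applies.

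**Step 3: scale.** Inputs: 45 per group (Sample size); transfused bleeding in 3/21 with stricturotomy and 0/164 with dilation (retrospective comparison table under Criteria).

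- Transfused bleeds expected in the EST arm at that rate: 45 × 3/21 = 6.4. All are major under the current wording.
- The rate r of conservatively managed, procedure-related readmission appears nowhere in the documents, so it is an assumption. Patients affected = 45 × r. Share of all such bleeds plus transfused bleeds = r / (14.3% + r), treating the readmissions as bleeds.

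| Assumed r in EST | Patients of 45 | Share |
|---|---|---|
| 0% | 0 | 0% |
| 2% | 0.9 | 12% |
| 5% | 2.25 | 26% |
| 10% | 4.5 | 41% |

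The share column is fragile. The 3/21 has an exact 95% confidence interval of about 3% to 36%, and those 21 patients had 45 procedures (45/21 = 2.1 each). Per procedure the rate is 4/45 = 8.9% (printed as 8.8%). The patient counts do not depend on 3/21.

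**The case against.** The strongest reply is that the text never says a readmission is minor. The qualifier can be read as covering bleeding and pain, and row 1 of the first table already shows length of stay overriding the minor list. On that view several days of inpatient care would not plainly be minor, and the case is merely unclassified. This stands in part: minor is the literal reading, not the only one. It does not remove the defect, because an outcome definition that unblinded assessors must complete case by case is still badly fixed.

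Second, the gap is narrow. Any readmission with perforation, transfusion or an intervention is already major. This stands in full.

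Third, nothing is lost, because adverse events are recorded for every patient and minor ones are part of the complications comparison. This stands as to the event. It does not stand as to the admission, for which no listed field or outcome exists.

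Fourth, the hospitalisation outcome is named as stricture-related and serves as an efficacy measure, while procedural harm belongs under complications. The retrospective table makes the same split. This stands: item 3 is not defective, and the repair belongs in item 4.

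Fifth, the documents give no discharge timing, and the delayed bleeding that clips are meant to prevent is not said to occur after discharge. This also stands, and it is one reason why the size cannot be fixed.

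**Conclusion.** The point holds in a limited form. Procedure-related readmission is missing from the major criterion. On the plain reading, a readmission for bleeding or pain managed without transfusion or intervention is graded minor, and no other outcome counts it. Such events may be under-graded, more likely in the EST arm because the protocol expects more bleeding there. The direction rests on that expectation. The size is unknown, and the 0 to 4.5 of 45 range is illustration only.

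A reader might go further and infer that the main expected harm of stricturotomy is understated. The documents do not support this: the only bleeding harm they quantify is transfused bleeding, which is major whenever it occurs.

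A reader might also try to scale the problem from 3/21 against 0/164. That needs a ratio of non-transfused readmissions to transfused bleeds, which the documents do not give. Nor does 0/164 transfused bleeds show that readmission for minor bleeding or pain is absent after dilation.

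Variation in discharge practice between centres is not an issue in a single-centre trial. The primary outcome and the sample size are untouched.

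**What to change.** - In the Definitions paragraph and in item 4 of Secondary outcome measures, change the major criterion to: *procedure-related prolongation of hospitalisation or any procedure-related unplanned admission or readmission*. Leave the perforation, transfusion and intervention criteria as they are.
- In both places, state that minor events, bleeding and pain included, involve neither. This also settles what the closing qualifier covers.
- Add one field to the data form for procedure-related admissions, since the listed items include only stricture-related ones.
- Keep item 3 as stricture-related hospitalisation, and report procedure-related admissions by arm under complications (item 4).

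The cost is two changes of wording and one form field, best made before enrolment so that every patient is recorded the same way. The stated major-event rate may rise, mainly in the EST arm.

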### **Sample size**

Based on previous retrospective study, symptomatic improvement with EST and EBD (9.5% and 33.5% respectively, the estimated sample size is total 90 (45 in each group) keeping type 1 error as 0.05 and power as 80%.

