### **Data analysis**

Statistical analysis: Statistical analysis would be done by using statistical package for social sciences (SPSS, IBM, NY, USA). Chi-square/Fisher's exact test was used to

compare categorical variables and Mann-Whitney test would be used to compare continuous variables between the two groups. P-value  $<0.05$  would be considered statistically significant

**Timeline:** 2 years

Recruitment of 100 CD patients with stenosis requiring EBD or EST over 1 years: follow up over 1 year.

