## Outcome measures

### Primary outcome measures

To compare sustained clinical improvement post EBD and ES (%) (time frame :

1 year): percentage of patients having no obstructive symptoms due to CD related stenosis for which EBD/ES was performed for a period of 1 year

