## Criteria

Outcome	Stricturotomy (n=21)	Balloon Dilation (n=164)	P value
Follow-up time, year	0.8 (0.1–1.6)	4.0 (0.8–6.9)	<0.001
Age at procedure, year	43.3 ± 14.5	42.8 ± 13.4	0.76
Duration from last surgery to procedure, year	6.4 (1.7–16.4)	7.8 (3.6–13.3)	0.56
Duration from CD diagnosis to procedure, year	19.6 (11.4–8.1)	16.6 (9.9–25.8)	0.85
Immediate technical success	21 (100.0%)	147 (89.5%)	0.25
Symptomatic improvement	8/11 (72.7%)	59/103(45.4%)	0.08
Endoscopic improvement	8/17 (47.1%)	57/163(35.0%)	0.32
Escalation of drug after procedure	13 (61.9%)	53 (32.3%)	0.09
Additional endoscopic therapy (EBD or ES)	6 (28.6%)	98 (59.8%)	0.85
Outcome	Stricturotomy (N=21)	Balloon Dilation (n=164)	P value
Disease related emergency department visits	2 (9.5%)	40 (24.4%)	0.74
Stricture-related	Per Patients	1 (2.0)	34 (20.7%)
	Per visit	4/11 (36.4%)	78/104(75.0%)
Disease related hospitalization		7 (33.3%)	40 (24.4%)
Stricture related	Per Patients	1 (4.8%)	33 (20.1%)
	Per visit	2/12 (16.7%)	57/102(55.9%)
Complication			
Perforation	Per patients	0/21 (0.0%)	4/164 (2.4%)
	Per procedures	0/45 (0.0%)	5/478 (1.1%)
Transfusion required bleeding	Per patients	3/21 (14.3%)	0/164 (0.0%)
	Per procedures	4/45 (8.8%)	0/478 (0.0%)
Subsequent surgery		2 (9.5%)	55 (33.5%)
			0.03

5-year surgery-free survival curve after treated with endoscopic strictureotomy (ES) versus endoscopic balloon dilation (EBD).

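### The sample size uses 9.5% and 33.5% as symptomatic improvement, but these are subsequent-surgery rates, so the stated 80% power has no basis for the primary outcome

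*Protocol*

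**What the plan says.** The Sample size section cites a previous retrospective study for "symptomatic improvement with EST and EBD (9.5% and 33.5% respectively, the estimated sample size is total 90 (45 in each group"). The significance level there is 0.05 and the target power 80%. The section gives neither the formula nor whether the test is one- or two-sided.

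The primary outcome (Primary outcome measures) is the "percentage of patients having no obstructive symptoms due to CD related stenosis for which EBD/ES was performed for a period of 1 year". The Definitions paragraph sets improvement after the procedure (clinical success) apart from the longer-term result: "Sustained clinical success was defined as absence of obstructive symptoms at 1 year follow up".

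Surgery is not part of the primary outcome. It appears within the first secondary outcome: "To compare need for additional intervention (EBD/EST/Surgery) between EST and EBD arm".

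The background table under Criteria compares stricturotomy (n=21) with balloon dilation (n=164). The rows that matter here are:

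| Row | Stricturotomy | Balloon dilation |
|---|---|---|
| Follow-up, years | 0.8 (0.1–1.6) | 4.0 (0.8–6.9) |
| Symptomatic improvement | 8/11 (72.7%) | 59/103 (45.4%) |
| "Subsequent surgery" | 2 (9.5%) | 55 (33.5%) |

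Planned enrolment is larger than the calculated 90. The Timeline under Data analysis reads "Recruitment of 100 CD patients with stenosis requiring EBD or EST over 1 years", and Study design also gives 100 patients.

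**The concern.** The two rates carry the label of one outcome and the values of another. Read literally, the Sample size section says that dilation improves symptoms about three and a half times as often as stricturotomy (33.5/9.5 = 3.5). That reverses the rationale in the Brief Summary and the table's own improvement row.

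The rates are also crude percentages over very different observation times, so they are not 1-year surgery rates either. Part of the 24-point gap may only reflect that dilation patients were watched about five times as long (4.0/0.8 = 5).

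The 45 per group and 80% power are the protocol's only statement of what the trial can detect. If they refer to another event, the reader cannot tell what difference in 1-year symptom-free rates the trial is able to show. A null primary result could then be read as coming from an 80%-powered trial when nothing supports that figure.

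**Working it through.** **Formula.** Two proportions, 1:1 allocation, two-sided α = 0.05, pooled variance under the null, no continuity correction, with p̄ = (p₁+p₂)/2:

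- n per arm = [1.960·√(2p̄(1−p̄)) + 0.842·√(p₁(1−p₁)+p₂(1−p₂))]² / (p₁−p₂)²
- power = Φ{[|p₁−p₂|·√n − 1.960·√(2p̄(1−p̄))] / √(p₁(1−p₁)+p₂(1−p₂))}

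**1. The plan's own figure.** With p₁ = 0.095 and p₂ = 0.335, p̄ = 0.215.

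- n = (1.1387 + 0.4676)² / 0.24² = 2.580/0.0576 = 44.8, so 45 per arm and 90 in total.
- Power at 45 per arm: (0.24·√45 − 1.1387)/0.5557 = 0.848, and Φ(0.848) = 80.2%.

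The stated 90 reproduces exactly, so these two rates did produce it.

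**2. Where the rates come from.** 2/21 = 9.5% and 55/164 = 33.5%, both in the surgery row. The value 33.5% stands in no other row. The value 9.5% also appears for emergency visits after stricturotomy, but there it is paired with 24.4%.

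**3. The table's improvement row as a rough proxy.** With 0.727 and 0.454, p̄ = 0.5905.

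- n = (1.3630 + 0.5623)² / 0.273² = 3.707/0.0745 = 49.7, so 50 per arm.
- Power is 75.8% at 45 per arm and 80.2% at 50 per arm.
- With 10% loss (an assumption), 50 × 0.90 = 45 evaluable per arm, which returns power to 76%.

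This row records improvement, not 1 year without obstructive symptoms. Its stricturotomy rate rests on 8/11, with an exact 95% interval of 39% to 94%.

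**4. The dilation cell in that row is inconsistent.** 59/103 is 57.3%, whereas 45.4% equals 59/130. The printed p of 0.08 agrees with 59/130 (uncorrected chi-square p = 0.081) and not with 59/103 (p = 0.32). If 59/103 were nevertheless right, 149 per arm would be needed, and power would be 33% at 45 and 36% at 50 per arm.

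**5. Illustrative range.** The Brief Summary says of dilation that "roughly half had recurrent symptoms and two third require surgery after EBD", without a time frame. Taking 50% symptom-free at 1 year after dilation as an assumption prompted by that remark:

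| Stricturotomy symptom-free (assumed) | Per arm for 80% | Power, 90 patients | Power, 100 patients |
|---|---|---|---|
| 70% | 93 | 49% | 53% |
| 74% | 64 | 65% | 70% |
| 80% | 39 | 86% | 89% |

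The 74% row keeps the 24-point gap and moves only the base rates. It shows that the same difference does not carry the same power. It is not a prediction of the effect.

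**The case against.** **The trial may be large enough anyway.** On the printed improvement percentages, the planned 100 patients give 80% power before dropout. This stands: a shortfall in patients is not shown. It does not rescue the stated justification, because the proxy is a different measure, rests on 11 stricturotomy patients and contains an inconsistent cell.

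**Power is the same for complements.** Surgery-free rates of 90.5% vs 66.5% also give 45 per arm. That is true, but it helps only if surgery-free is equated with symptom-free, which the protocol never does.

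**The illustrative rates are chosen, not sourced.** This is fair. They show how much power depends on inputs the protocol does not give, and nothing more. The 24-point gap in particular should not be read as an expected 1-year effect.

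**The p-value argument for 59/130 is limited.** Other rows fit no single test. Drug escalation, for example, gives an uncorrected p of 0.008 against a printed 0.09, and additional endoscopic therapy gives 0.007 against 0.85. So 59/130 is a plausible reading that needs checking at the source, and the cell is not an input to the sample size.

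**The exact match depends on the method.** With a continuity correction the formula gives 53 per arm. Fisher's exact test, which Data analysis also allows, has about 74% power at 45 per arm for the stated rates. The Sample size section does not cite the table by name either, so the link is an inference. A unique match on both percentages makes it a strong one.

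**Conclusion.** The Sample size section is wrong as written and must be corrected. The rates it calls symptomatic improvement are the table's subsequent-surgery rates, and its 45 per group and 80% power describe that event. They do not describe 1-year freedom from obstructive symptoms.

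The actual power for the primary outcome cannot be fixed from this document. It is about 76% to 80% on the printed improvement percentages (90 to 100 evaluable patients). It runs from 49% to 89% over the illustrative rates, which rest on an assumed 50% symptom-free after dilation. All these figures assume a two-sided 5% test without continuity correction. Confidence in the mislabelling is high. The size of any power loss is unknown.

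**What to change.** In the Sample size section, remove 9.5% and 33.5% as symptomatic improvement. State the assumed 1-year symptom-free rate in each arm with its source, name the formula and sidedness, and restate power for the primary outcome at both 90 and 100 patients over a range of rates. Possible wording:

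> The primary outcome is the proportion of patients free of obstructive symptoms for 1 year. We assume X% after EST and Y% after EBD [source]. With a two-sided 5% test, power is A% with 90 and B% with 100 evaluable patients. The table below gives power over a range of rates.

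If the table's improvement row is used as support, call it a proxy, and first check 59/103 (45.4%) against its source. Do not carry the 24-point surgery gap over as a 1-year effect, given the unequal follow-up.

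The cost is one rewritten paragraph and a short table. The restated power may be less favourable, and whether 90 or 100 patients suffice depends on the rates then assumed.
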